## 7.5 Study Size

**Sample Size and Power:** Estimated power to evaluate the primary objective (i.e., hypothesis that JoRRP risk is lower among children whose biologic mother was fully vaccinated with GARDASIL or GARDASIL 9 one year prior to delivery versus those unvaccinated) is presented in this section. The statistical criterion for success requires that the odds ratio be  $\geq 3.0$  and lower bound of the 95% confidence interval for the odds ratio be  $\geq 1.33$ . Based on available information, the Sponsor's power calculations (summarized below) support testing of this hypothesis; however, the exact number of cases is not known and therefore a decision to conduct the analysis will be made once data are received from the registries.

The estimated number of possible JoRRP cases (identified using ICD-10 code D14.1) occurring after GARDASIL introduction in Sweden, Denmark, and Norway (among children

PRODUCT: V501/V503	PROTOCOL/AMENDMENT VERSION NO.: V503-095-00-v3
REVOPS ID NO: NIS102781	CORE DRC APPROVAL DATE: 18MAR2024
EPIDEMIOLOGY NO.(PE STUDIES ONLY): 08039.022	

born to mothers with opportunity to receive HPV vaccination prior to delivery; birth cohorts 2008 to 2020) is approximately 100, 50, and 50, respectively (total=200). Study power was estimated according to varying number of cases (100 to 300) and effect size (odds ratio from 3 to 4) and overall female vaccination exposure rate (5% to 10%) in the maternal birth cohorts of interest, with constant alpha-level of 0.05, and control/case ratio of 10 or 100 [Table 1]. With 200 cases originating from 2008-2020 birth cohorts, the estimated power assuming true odds ratio of 3.0 is 92% (10 controls per case) and 94% (100 controls per case). Precision was also taken into account by specifying that the analyses for the primary objective be powered to detect an odds ratio of at least 3.0, with a lower bound for the confidence interval of at least 1.33, which is equivalent to lower bound of 95% confidence interval of vaccine effectiveness  $\geq 25\%$ . This level of precision is attainable within the study power calculation assuming  $\geq 120$  incident JoRRP cases are observed (with 100 controls per case) or  $\geq 140$  incident JoRRP cases are observed (with 10 controls per case) in the cohort of interest. Herd protection was not considered in evaluation of study power for two reasons: 1) In the Nordic region, the average maternal age at birth of first child is ~29 years and in older birth cohorts vaccination rates are much lower, and 2) Males, who are typically the vectors of infection, were not targeted for vaccination until very recently. To examine the potential effect of herd protection and test this assumption, age-standardized incidence rates of JoRRP will be calculated according to maternal vaccination status to assess changes in incidence in pre- and post-vaccination periods among children of unvaccinated mothers, e.g., through calculation of annual percent change.

It is important to note that these approximate counts were generated for the purpose of power estimation only through accessing publicly available gross statistics on ICD codes for otorhinolaryngological diseases, and that no preliminary analyses evaluating the association between HPV vaccination and RRP have been performed.

In observational studies, high effect estimates are considered important to demonstrate strong associations and to assess causality. Conventionally, relative risks of  $< 2$  are considered to represent weaker associations by epidemiologists, as it may not be possible to judge whether or not the association can be entirely accounted for by bias [34]. A threshold of 3.0 is therefore proposed to establish the effectiveness of GARDASIL/GARDASIL 9 vaccination in preventing JoRRP. Prior Nordic registry studies reported GARDASIL effectiveness against genital warts ranging from 38%-88% (equivalent to ORs of 1.6-8.3) and cervical intraepithelial neoplasia grade 2+ ranging from 22%-75% (equivalent to ORs of 1.3-4.0) with higher effect among females vaccinated at younger age. Based on the preliminary possible JoRRP case counts for Sweden, Denmark and Norway provided by the study Principal Investigators ([name] from Karolinska Institutet, [name] from Danish Cancer Society Research Center, and [name] from Cancer Registry of Norway), this study is expected to be sufficiently powered to assess GARDASIL/GARDASIL 9 vaccine effectiveness against JoRRP [Table 1]; however, this will need to be re-evaluated once actual number of cases is confirmed. The power of the study will be calculated once data are received from the registries, and the exact number of cases occurring in relevant birth cohorts is determined. This assessment of whether the study is adequately powered to proceed with addressing the study primary objective will be made

PRODUCT: V501/V503	PROTOCOL/AMENDMENT VERSION NO.: V503-095-00-v3
REVOPS ID NO: NIS102781	CORE DRC APPROVAL DATE: 18MAR2024
EPIDEMIOLOGY NO.(PE STUDIES ONLY): 08039.022	

prior to conducting any analyses and without knowledge of mothers' vaccination status of cases. If due to low number of cases, study power is not sufficient, then the analysis will not be performed until adequate cases are available in the Nordic Registries or until a point at which the feasibility of accruing sufficient cases would need to be reassessed.

Table 1 Power Estimates According to Varying Number of Cases of JoRRP (From 100 to 300), Effect Size (Odds Ratio From 3.0 to 4.0), and Vaccination Coverage (5% to 10%), With Constant Alpha-Level of 0.05, Lower Bound of 95% Confidence Interval >1.33, And Control/Case Ratio of 10 or 100

True Effect Size	Vaccine Coverage	Cases of JoRRP							
		100	125	150	175	200	225	250	300
Control/case ratio of 10									
OR=3	5%	0.68	0.76	0.82	0.87	0.92	0.93	0.96	0.98
	10%	0.86	0.93	0.92	0.98	0.99	0.99	1	1
OR=3.5	5%	0.83	0.90	0.93	0.96	0.98	0.99	0.99	1
	10%	0.96	0.99	0.99	1	1	1	1	1
OR=4	5%	0.92	0.96	0.98	0.99	1	1	1	1
	10%	0.99	1	1	1	1	1	1	1
Control/case ratio of 100									
OR=3	5%	0.72	0.80	0.86	0.91	0.94	0.96	0.97	0.98
	10%	0.90	0.95	0.98	0.99	0.99	1	1	1
OR=3.5	5%	0.86	0.92	0.96	0.97	0.99	0.99	1	1
	10%	0.98	0.99	1	1	1	1	1	1
OR=4	5%	0.95	0.98	0.99	1	1	1	1	1
	10%	0.99	1	1	1	1	1	1	1

**Note:** For OR=3 and 5% vaccination coverage, >80% power would be achieved with 140 cases with 10 controls per case and 120 cases with 100 controls per case.

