## 6 RESEARCH QUESTION AND OBJECTIVES

### 6.1 Primary Objective

To assess if the odds of JoRRP are lower among children whose biologic mothers were fully vaccinated with GARDASIL/GARDASIL 9 at least one year prior to delivery versus unvaccinated mothers.\*

\* In case-control studies, the odds (likelihood) of exposure are typically assessed among cases of a disease and compared with controls. However, given that the odds ratio is the same regardless of how it is defined in terms of marginal probabilities, i.e., probability of exposure given disease or probability of disease given exposure are statistically equivalent, we have chosen to express it as the latter (probability of disease given exposure) to provide a measure of the protective effect of vaccination against JoRRP. Additionally, given the rare outcome of JoRRP and the use of incidence density sampling, odds ratio estimates will be interpreted as the corresponding relative risks.

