### 7.8.2 Primary Objective: Calculation of Epidemiological Measures of Interest

Descriptive statistics will be calculated for the cases and controls in terms of age of child at diagnosis, age of mother at the time of delivery, mode of delivery, maternal genital warts history, maternal smoking status, education level (mother), family income, and mother's

PRODUCT: V501/V503	PROTOCOL/AMENDMENT VERSION NO.: V503-095-00-v3
REVOPS ID NO: NIS102781	CORE DRC APPROVAL DATE: 18MAR2024
EPIDEMIOLOGY NO.(PE STUDIES ONLY): 08039.022	

country of birth using t-test or chi-2-test for differences in continuous and categorical variables, as appropriate. Conditional logistic regression will be conducted for estimation of ORs and corresponding 95% confidence intervals, with adjustment for relevant covariates. For a detailed discussion of covariates of interest, please see Annex 1, which lists subject matter expertise analysis of the association of interest, and potential confounding thereto. Annex 1 also motivates closely the inclusion of covariates described here below.

In case-control studies, it is actually the odds of exposure which is typically assessed among cases of a disease and then compared with odds of exposure among controls. However, the odds ratio is the same regardless of how it is defined in terms of marginal probabilities, i.e., probability of exposure given disease or probability of disease given exposure are statistically and technically equivalent. As per standard practice, it was therefore chosen to express ORs as the probability of disease given exposure, to provide a measure of the association between vaccine receipt and disease outcome.

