### 7.8.3 Exploratory Objectives: Calculation of Epidemiological Measures of Interest

Risk factors for JoRRP will be explored in the VE analysis conditional logistic regression model to evaluate if they are independently statistically significantly associated with the outcome of JoRRP, with all other factors held constant. Specifically, vaccination exposure will be at the reference level (i.e., unvaccinated).

Information will be presented on biological mother-child pairs, focusing on concordant and discordant pairs for JoRRP and AoRRP (history of diagnosis, identified using ICD-10 code D14.1), e.g., preparation of summary 2x2 table (if possible). Due to strict data protection regulation in Europe, it is not possible to include exact counts if <5 in an individual cell.

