## 12 ANNEXES

### Annex 1 OVERVIEW OF POTENTIAL CONFOUNDING IN ASSESSMENT OF HPV VACCINE EFFECTIVENESS AGAINST JUVENILE-ONSET RRP

#### **Definitions:**

[figure not shown]
Study exposure: Maternal HPV vaccination with GARDASIL or GARDASIL 9, below called HPV vaccination.

Study outcome: Juvenile-onset recurrent respiratory papillomatosis.

Primary objective: Estimate odds ratio (OR) of JoRRP (yes/no) given HPV vaccination in biologic mother (yes/no).

Power: The study has >80% power to detect an OR of 3.0 with a lower bound of the 95% confidence interval of >1.33, assuming at least 120 cases of JoRRP are observed.

Main association of interest:

The hypothesis is that maternal HPV vaccination is negatively associated with the odds (likelihood) of JoRRP. Factors that may act as confounders to this association are considered, below. That is, factors associated with both exposure and outcome in such a way that an observed association between the two is partially or completely confounded. Given that causal HPV infections in cases of JoRRP are acquired vertically (from mother-to-child during delivery), many of the same factors considered here as confounders in evaluating the association between HPV vaccination and JoRRP are the same as those considered in evaluating the association between HPV vaccination and AoRRP.

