## Annex 2 TABLE AND FIGURE SHELLS FOR RRP STUDY (PRIMARY OBJECTIVE)

Table 2 Characteristics of Study Population, JoRRP Cases, and Control Subjects (prepared separately for each country)

	Study population, No. (%)	JoRRP cases, No. (%)	Controls, No. (%)
Age of child , years, mean (SD)			
Age of mother at delivery , years, mean (SD)			
Highest level of education achieved by mother*			
Low			
Medium			
High			
Missing			
Highest annual household family income level‡			
Low			
Medium			
High			
Missing			
Mother's country of birth			
Current country of residence			
Other country			
Missing			
Method of delivery			
Vaginal			
Cesarean			
Missing			
Maternal history of EGW			
Yes			
No			
Missing			
Maternal smoking status at first prenatal visit			
Yes			
No			
Missing			

EGW = external genital warts; JoRRP = juvenile-onset recurrent respiratory papillomatosis; SD = standard deviation

\*Education level of mother at index date.

‡Based on average level between 2006 (the start year of HPV vaccination) and the index date.

PRODUCT: V501/V503	PROTOCOL/AMENDMENT VERSION NO.: V503-095-00-v3
REVOPS ID NO: NIS102781	CORE DRC APPROVAL DATE: 18MAR2024
EPIDEMIOLOGY NO.(PE STUDIES ONLY): 08039.022	

Table 3 Number of Cases and Odds Ratio for Recurrent Respiratory Papillomatosis (RRP) by GARDASIL/GARDASIL 9 Vaccination Status, 2008-2020

GARDASIL/ GARDASIL 9 vaccination status	JoRRP (ICD-10 code: D14.1)			
	No. of cases 	No. of controls 	Crude OR (95% CI)	Adjusted OR  (95% CI)
Fully Vaccinated 			Ref.	Ref.
Unvaccinated				

*CI = confidence interval; HPV = human papillomavirus; ICD-10 = international classification of disease, 10th modification; JoRRP = juvenile-onset recurrent respiratory papillomatosis; OR = odds ratio; Ref. = reference.*

 All study participants who acquired a first diagnosis of D14.1 before age 10 years and appropriate topography/morphology code (if available from pathology/cancer registry).

 Up to 100 controls matched on age of mother, sex of subject, and region of diagnosis.

 Adjustment factors considered for inclusion include maternal education level, family income level, maternal smoking status, mother's country of birth, and method of delivery.

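### The 7.5 success rule names no reference group, Annex 1 defines the odds ratio the opposite way, and Table 1 reproduces only in the direction of harm, so the stated 92–94% power does not apply to the intended test

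*Protocol*

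**What the plan says.** Section 7.5 opens with the "hypothesis that JoRRP risk is lower among children whose biologic mother was fully vaccinated" compared with children of unvaccinated mothers. It then gives the decision rule: "The statistical criterion for success requires that the odds ratio be" at least 3.0 and the "lower bound of the 95% confidence interval for the odds ratio be" at least 1.33. Neither sentence names a numerator or a reference group.

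Elsewhere the protocol points in two directions.

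- **Unvaccinated versus vaccinated (protection gives OR above 1).** The Abstract and 7.5 equate the 1.33 limit with 25% vaccine effectiveness. Section 7.5 also converts effectiveness of 38%–88% to ORs of 1.6–8.3, and 22%–75% to 1.3–4.0. The Table 3 shell in Annex 2 marks the "Fully Vaccinated" row as the reference.
- **Vaccinated versus unvaccinated (protection gives OR below 1).** Annex 1 has: "Primary objective: Estimate odds ratio (OR) of JoRRP (yes/no) given HPV vaccination in biologic mother (yes/no". It adds that the association is expected to be negative. Less explicitly, 7.8.2 says "it was therefore chosen to express ORs as the probability of disease given exposure", and the note to 6.1 uses the same device, "probability of disease given exposure) to provide a measure of the protective effect of vaccination against JoRRP". Section 7.1 classifies the vaccinated mother as exposed.

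The same list of definitions in Annex 1 then claims more than 80% power for an OR of 3.0 with a lower limit above 1.33, given at least 120 cases.

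Table 1 gives power at OR 3 with 200 cases as 0.92 (10 controls per case) and 0.94 (100 per case) at 5% coverage, and 0.99 for both ratios at 10%. Section 7.5 makes performing the analysis depend on power being sufficient once the case count is known.

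**The concern.** A pre-specified decision rule should give the same verdict whichever section the analyst follows, and this one does not. Take an illustrative result of 75% effectiveness with 95% limits of 50% and 87.5%. Coded as in Table 3, the OR is 4.0 (2.0 to 8.0) and the study succeeds. Coded as Annex 1 words it, the OR is 0.25 (0.125 to 0.50) and the rule as written is not met. The limit that matters also changes, because the lower limit of one OR is the reciprocal of the upper limit of the other.

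The second stake is larger. Power to show that a factor with 5% prevalence triples risk is not the power to show that it cuts risk to a third. Protection leaves very few exposed cases. If Table 1 was computed in the wrong direction, the check on whether to proceed would clear a study that is badly underpowered for its own rule.

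**Working it through.** **1. Direction implied by the conversions in 7.5.** With OR for unvaccinated versus vaccinated, VE = 1 − 1/OR.
- 1 − 1/1.33 = 24.8%, the stated 25%.
- 1/(1 − 0.38) = 1.6 and 1/(1 − 0.88) = 8.3, as stated.
- 1/(1 − 0.22) = 1.3 and 1/(1 − 0.75) = 4.0, as stated.

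So 7.5 intends unvaccinated versus vaccinated. On the inverse scale the rule is OR ≤ 1/3.0 = 0.333 with upper limit ≤ 1/1.33 = 0.752.

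**2. Set-up for power.** Unmatched 2×2 table; coverage p0 taken as the exposure prevalence in controls; Wald 95% limits on the log OR, with 0.5 added only if a cell is zero; success when the lower limit is at least 1.33; 200,000 simulated studies per cell. Exposure among cases is p1 = p0·OR / (1 − p0 + p0·OR).

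**3. Reproducing Table 1.** Take vaccinated versus unvaccinated OR = 3 (harm), p0 = 0.05: p1 = 0.15/1.10 = 0.136, or about 27 vaccinated mothers among 200 cases.

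| OR 3, 5% coverage | 100 | 125 | 150 | 175 | 200 | 225 | 250 | 300 |
|---|---|---|---|---|---|---|---|---|
| 10:1 stated | 0.68 | 0.76 | 0.82 | 0.87 | 0.92 | 0.93 | 0.96 | 0.98 |
| 10:1 computed | 0.67 | 0.76 | 0.82 | 0.87 | 0.91 | 0.93 | 0.95 | 0.98 |
| 100:1 stated | 0.72 | 0.80 | 0.86 | 0.91 | 0.94 | 0.96 | 0.97 | 0.98 |
| 100:1 computed | 0.72 | 0.80 | 0.86 | 0.90 | 0.93 | 0.96 | 0.97 | 0.99 |

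The other rows that were run agree within 0.02, apart from one cell (OR 3, 10% coverage, 150 cases, 10:1: stated 0.92, computed 0.96). That cell also breaks the order of its own row and may be a typing error. The two-sided 95% limits are therefore applied as stated; the direction is the problem.

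**4. The intended direction.** Take vaccinated versus unvaccinated OR = 1/3, inverted before the rule is applied. At p0 = 0.05, p1 = 0.01667/0.96667 = 0.0172, so 200 × 0.0172 = 3.4 vaccinated mothers are expected among 200 cases. At p0 = 0.10, p1 = 0.0357, or 7.1.

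| 200 cases, true VE 67% | Stated | Simulated | Closed form |
|---|---|---|---|
| 5%, 10:1 | 0.92 | 0.17 | 0.31 |
| 5%, 100:1 | 0.94 | 0.15 | 0.32 |
| 10%, 10:1 | 0.99 | 0.60 | 0.55 |
| 10%, 100:1 | 0.99 | 0.62 | 0.57 |

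The closed form is Φ[(ln 3 − ln 1.33)/SE − 1.96]. At 5% and 100:1, SE = 0.544, so 0.8134/0.544 − 1.96 = −0.465 and Φ = 0.32. Simulation and closed form differ at 5% because the vaccinated-case cell is so small. With controls at exactly 5% and 100:1, one vaccinated case gives OR 10.5 with lower limit 1.47 (success), but two give 5.2 with lower limit 1.29 (failure).

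With a stronger effect (vaccinated versus unvaccinated OR 1/4, 5% coverage, 200 cases), simulated power is 0.28 (10:1) and 0.26 (100:1), against a stated 1.00 for OR 4.

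**5. The case thresholds.** Section 7.5 gives 120 cases (100:1) and 140 cases (10:1) for at least 80% power. In the intended direction the closed form gives 21% and 23%. The simulation gives 0.00 at 125 cases (100:1) and 0.01 at 150 cases (10:1). For 80% power, SE must fall to 0.8134/(1.96 + 0.842) = 0.290, so n = 200 × (SE at 200 cases / 0.290)². That is about 726 cases (10:1) or 703 (100:1) at 5% coverage, and 358 or 346 at 10%.

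**6. The literal rule on the Annex 1 scale.** With true vaccinated versus unvaccinated OR 1/3, 0 of 200,000 simulated studies met it (200 cases, 100:1, 5%).

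**The case against.** The strongest reply is that the intended direction is not in doubt. Section 7.5 calls 3.0 the threshold to establish effectiveness, every conversion to vaccine effectiveness uses the inverse OR, and the shell for the primary result sets the fully vaccinated as reference. This stands. A reader might infer that the rule condemns any protective vaccine to failure, or would let a harmful one succeed; that requires setting aside the Abstract, 7.5 and Table 3, and the documents do not support it.

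It is also fair that the passages on the other side are uneven. The wording in 6.1 and 7.8.2 mainly argues that the OR is the same whether one conditions on disease or on exposure; it sets no reference category. Section 7.8.3 says "Specifically, vaccination exposure will be at the reference level (i.e., unvaccinated"), which could be taken as fixing the coding of the primary model, but it concerns the exploratory risk-factor ORs with vaccination held at one level. Annex 1 is the one clear conflict, since it holds both conventions in a single list.

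On power, one could say that the arithmetic of Table 1 would also fit an OR of 3 for unvaccinated mothers if 5% were the share unvaccinated. That is numerically true, but 7.5 and Table 1 call the 5%–10% vaccination exposure and vaccination coverage. What remains after these replies is a decision rule whose direction must be inferred and a power table that does not match the inferred direction.

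**Conclusion.** The concern holds as an unreconciled decision rule with a material consequence for power. The direction can be recovered as unvaccinated versus fully vaccinated, but the rule itself does not state it and Annex 1 contradicts it. In that direction the stated power is not supported. With 200 cases and 67% true effectiveness, power for the lower-limit condition is about 15–17% at 5% coverage by simulation (31–32% in closed form) and about 60–62% at 10%, against 92–94% and 99%.

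These figures rest on an unmatched table, Wald limits, and coverage equal to exposure among controls. Those assumptions are supported by how closely they reproduce Table 1 in the other direction. Matching and covariate adjustment were not modelled. The exact value at 5% coverage depends on how limits are computed with three or four expected vaccinated cases, but both methods fall far short of the stated figures. The power figures, like Table 1, reflect the lower-limit condition alone, without the further requirement that the point estimate reach 3.0.

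**What to change.** In the Abstract, 7.5 and Annex 1, state the rule with its direction: OR for unvaccinated versus fully vaccinated at least 3.0 with lower 95% limit at least 1.33; equivalently, OR for fully vaccinated versus unvaccinated at most 0.33 with upper 95% limit at most 0.75. Use the same comparison wherever the OR is defined, in 6.1, 7.8.2 and the Annex 1 definitions, and label the OR columns of Table 3 to match.

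Then recompute Table 1, the 92% and 94% figures, and the 120- and 140-case thresholds (including the Annex 1 power statement) for a protective effect at the stated coverages. Restate them before the decision in 7.5 on whether to perform the analysis, and while vaccination status of the cases' mothers is still unknown, as 7.5 already requires.

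The cost is wording in a handful of places and one power recalculation, with no new data. The sponsor should expect the restated power to be much less favourable, which bears directly on whether about 200 cases are enough.

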## 2 ABSTRACT

Title	Nested case-control study evaluating effectiveness of immunization of girls and women of childbearing potential with GARDASIL™/GARDASIL™ 9 against juvenile-onset recurrent respiratory papillomatosis (JoRRP) in Sweden, Denmark, and Norway
Protocol Number / Version	V503-095-00-v3
Date	18Mar2024
Authors	PPD PPD
Rationale & Background	Recurrent respiratory papillomatosis (RRP) is a medical condition where HPV types 6 and 11 cause wart-like growths in the larynx. The condition is rarely fatal but associated with high morbidity. Current treatment only offers temporary symptomatic relief. There is an expectation that HPV vaccination of mothers, targeting types 6 and 11, will reduce incidence of RRP in their children.
Research Question(s) & Objective(s)	Primary Objective: To assess if the odds of JoRRP are lower among children whose biologic mothers were fully vaccinated with GARDASIL/GARDASIL 9 at least one year prior to delivery versus unvaccinated mothers.
Study Design	Population-based nested case-control study
Population	Primary objective: Children 0-9 years of age between 2008 and 2018 or later, born to mothers with opportunity to receive GARDASIL/GARDASIL 9, i.e. birth cohorts 2008 to 2018+.

PRODUCT: V501/V503	PROTOCOL/AMENDMENT VERSION NO.: V503-095-00-v3
REVOPS ID NO: NIS102781 EPIDEMIOLOGY NO.(PE STUDIES ONLY): 08039.022	CORE DRC APPROVAL DATE: 18MAR2024

Variables	
Exposure definition: Fully vaccinated with GARDASIL/GARDASIL 9 according to schedule (2 or 3 doses according to age at vaccination) in biologic mother of child.
 
Outcome definitions:
 
 
- First diagnosis of JoRRP from national registries using ICD-10 code D14.1 (benign neoplasm of larynx).
 

Data Sources	Nordic population, patient, and vaccine registries.
Study Size	
Primary objective (nested case-control study):
 
 
- JoRRP: ~200 cases, ~100 controls per case (i.e. ~20,000 controls)
 

Data Analysis	
Power calculation for primary objective (estimated 200 JoRRP cases and 20,000 controls)
 
JoRRP: study is 94% powered to detect a <math>RR \geq 3.0</math> with a lower bound of the 95% confidence interval of <math>>1.33</math>; equivalent to lower bound of 95% CI of vaccine effectiveness <math>>25\%</math> (sample size and study power to be confirmed prior to initiating analysis).

Milestones	Planned Date

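### Table 1 and the 92%/94% power treat vaccination as raising the odds of JoRRP threefold; for a protective OR of 3.0 at 5% coverage, power with 200 cases is about one third or less

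*Protocol*

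**What the plan says.** Section 7.5 states that, with 200 cases, "the estimated power assuming true odds ratio of 3.0 is 92% (10 controls per case) and 94% (100 controls per case". Table 1 shows these as the entries for an odds ratio of 3 and 5% vaccine coverage. The Abstract repeats the larger figure ("JoRRP: study is 94% powered to detect a" relative risk of at least 3.0). The note to Table 1 says that, at the same effect and coverage, more than 80% "power would be achieved with 140 cases with 10 controls per case and 120 cases with 100 controls per case". Annex 1 also claims more than 80% power, "assuming at least 120 cases of JoRRP are observed". All these figures refer to an estimate "with a lower bound for the confidence interval of at least 1.33".

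The protocol also fixes the direction of the odds ratio. The Annex 1 hypothesis is that "maternal HPV vaccination is negatively associated with the odds (likelihood) of JoRRP". Section 7.5 converts earlier vaccine effectiveness results "ranging from 38%-88% (equivalent to ORs of 1.6-8.3", which is OR = 1/(1 - VE), and equates a lower bound of 1.33 with 25% effectiveness. The Table 3 shell uses fully vaccinated as the reference row. An odds ratio of 3.0 is therefore unvaccinated versus vaccinated, and the odds ratio for vaccination is 1/3.

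**The concern.** Reversing an odds ratio changes nothing in a symmetric table, but it changes the power a great deal when the exposure is rare. If 5% of control mothers are vaccinated and vaccination protects, very few case mothers are vaccinated, and precision depends almost entirely on that small count. If the same 5% exposure triples the odds, the exposed cases are several times more numerous. A table computed in the second direction cannot describe the first.

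Section 7.5 makes the decision to analyse depend on whether the study is adequately powered. Repeating the same calculation with the confirmed case count would carry the error into that decision, and could start an analysis that expects only two or three vaccinated case mothers.

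**Working it through.** **Inputs** (section 7.5 and Table 1): 200 cases; 10 or 100 controls per case; coverage c = 5% or 10%, taken as coverage in controls; true OR 3.0; success if the lower limit of the two-sided 95% interval is at least 1.33. The main check uses an unmatched 2x2 table; matched conditional logistic regression is the cross-check.

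**1. Reproducing Table 1.** Let vaccination multiply the odds by 3. The vaccinated share of cases is 3c/(1 + 2c) = 0.15/1.10 = 13.6%, or 27.3 of 200. Simulated power with a Wald interval at 5% coverage:

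| Cases, controls per case | Simulated | Printed |
|---|---|---|
| 200, 100 | 0.935 | 0.94 |
| 200, 10 | 0.905 | 0.92 |
| 100, 100 | 0.723 | 0.72 |
| 100, 10 | 0.66 | 0.68 |

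In this direction 95 of the 96 cells agree within 2 percentage points. The exception is 0.92 at 150 cases (OR 3, 10% coverage, 10 controls per case). Simulation gives 0.96, and the printed value is out of sequence between 0.93 and 0.98.

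**2. Protective direction, 200 cases, 5% coverage, 100 controls per case.** The vaccinated share of cases is (c/3)/(1 - c + c/3) = 0.01667/0.96667 = 1.72%, or 3.45 of 200.

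- Var(log OR) = 1/3.45 + 1/196.55 + 1/1,000 + 1/19,000 = 0.296, so SE = 0.544. In step 1 the variance is 0.0435.
- Normal approximation: ln(3.0/1.33) = 0.813; 0.813/0.544 - 1.96 = -0.47; power 32%.
- Exact, control odds treated as fixed: at OR 1.33 the vaccinated share of cases is 3.8%. The criterion is met with 0, 1 or 2 vaccinated cases, which has probability 33% when the true OR is 3.0.
- Simulated Wald: 14%, or 17% if tables with no vaccinated case count as successes. Simulated conditional logistic regression: 14-15%.

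**3. Protective direction, 10% coverage.** The vaccinated share is 0.03333/0.93333 = 3.57%, or 7.1 of 200. Power is 57% (normal approximation), 58% (exact), 61% (simulated Wald and conditional logistic) and 71% (mid-P or profile likelihood). Table 1 prints 0.99.

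**4. The 120- and 140-case statement, 5% coverage.** Expected vaccinated case mothers: 120 x 1.72% = 2.1 and 140 x 1.72% = 2.4. Normal-approximation power is 21% (120 cases, 100 controls per case) and 23% (140 cases, 10 controls per case), against more than 80% stated.

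**5. Cases for 80% power, lower-bound criterion only, 100 controls per case.** n = V1 x [(1.96 + 0.8416)/0.813]^2, where V1 is the variance in step 2 multiplied by the number of cases. At 5% coverage V1 = 59.2 and n is about 700; at 10% V1 = 29.1 and n is about 350.

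**6. Other readings tried** (protective direction, 200 cases, 5%). One-sided 5%: 43-44%. Testing against 1 instead of 1.33: 51-61%. Taking 5% as coverage among cases: 69-71%. None reaches 92% or 94%. The printed values would fit a population with 5-10% of mothers *un*vaccinated, which contradicts the table's coverage label.

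**The case against.** The strongest reply is that the stated power is provisional. The Abstract says sample size and power are to be confirmed before analysis, and section 7.5 promises a recalculation once the registries deliver the case count. That is true, and it rules out one tempting inference. A reader might take 120 cases as a fixed go/no-go threshold, but the protocol presents 120 and 140 only as the counts said to give more than 80% power. However, the promised recalculation updates the number of cases. Nothing in it corrects the direction of the effect.

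A second reply is that the lowest corrected figures are unstable, and this also stands. With 2 vaccinated cases in 200 the OR is (0.05/0.95)/(2/198) = 5.2 and the SE about 0.71, so the Wald lower limit is about 1.29, just short of 1.33. At 5.2% coverage, Wald power rises to about 28-30%. The fair statement is one third or less. At 120 cases the answer ranges from 0% to 39% by method, which shows only that about two events carry little information.

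Third, a reader might infer that the information is overstated eightfold, or that every cell of Table 1 fails. Neither follows. The ratio 27.3/3.45 = 7.9 compares vaccinated cases; the variance ratio is 0.296/0.0435 = 6.8. At 200 cases, 10% coverage and OR 4, corrected power is about 71% (normal approximation) to 84% (simulated Wald), against 1 printed. The comparison at 5% coverage is still the relevant one, because the Abstract and the text of section 7.5 quote that row.

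**Conclusion.** The error is real, and the power statements are wrong as written. At OR 3.0 and 200 cases with 100 controls per case, power for the lower-bound criterion is about one third or less at 5% coverage (94% stated) and about 57-62% at 10% coverage, up to about 71% by mid-P or profile likelihood (99% stated). The claim of more than 80% power from 120 or 140 cases fails.

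This assumes that the stated coverage applies to control mothers and that there is no covariate adjustment. Matching makes little difference.

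A reader might infer that 700 cases at 5% coverage, or 350 at 10%, would make the study adequate. That holds for the lower bound only. Section 7.5 also requires the estimated odds ratio to be at least 3.0. When the true value is 3.0, that condition holds success near 50% whatever the case count, in either direction. Nor do the documents show that a missed criterion would be read as weak effectiveness: section 7.5 allows deferral, and section 7.3 provides for independent review of the interpretation.

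**What to change.** - Recompute Table 1 with the vaccinated share of cases equal to (c/OR)/(1 - c + c/OR), where c is coverage in controls. Prefer an exact or score method, because the expected counts are small.
- Restate the power, and the case count said to give more than 80%, in the Abstract, section 7.5, the note to Table 1 and Annex 1.
- Carry out the pre-analysis power assessment in section 7.5 in the protective direction, using the confirmed case count and the coverage observed in the matched controls. The vaccination status of the case mothers then stays unseen, as that section requires.
- Say whether the restated power covers only the lower-bound criterion or also the requirement that the odds ratio be at least 3.0.

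The cost is a rerun of the calculation and amended wording, with no new data. The stated power becomes much less favourable and may lead to the deferral that section 7.5 already allows.
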